13.5 Maximum cycles for patients who achieve CR/CMR

Patients who achieve a CR/CMR will receive a maximum total of 32 cycles (i.e 2 years of therapy). After 2 years, they should be observed (see Section 13.4 above).

13.6 Continuation of therapy after PR/PMR or SD

Patients who are in PR/PMR or SD will continue on therapy for a total of 2 years. After 2 years, they should be observed (see Section 13.4 above) until PD and then they will go to event monitoring (see Section 13.5 above). Subsequent treatment is at the discretion of their attending physician.

13.7 Definition of Ineligible

A patient is deemed *ineligible* if after registration, it is determined that at the time of registration, the patient did not satisfy each and every eligibility criteria for study entry. The patient may continue treatment off-protocol at the discretion of the physician as long as there are no safety concerns, and the patient was properly registered. The patient will go directly to the event-monitoring phase of the study (or off study, if applicable).

- If the patient received treatment, all data up until the point of confirmation of ineligibility must be submitted. Event monitoring will be required per Section 18.0 of the protocol.
- If the patient never received treatment, on-study material and the End of Active Treatment/Cancel Notification Form must be submitted. No further data submission is necessary.

13.8 Definition of Major Violation

A patient is deemed a *major violation*, if protocol requirements regarding treatment in Cycle 1 of the initial therapy are severely violated that evaluability for primary end point is questionable. All data up until the point of confirmation of a major violation must be submitted. The patient will go directly to the event-monitoring phase of the study. The patient may continue treatment off-protocol at the discretion of the physician as long as there are no safety concerns, and the patient was properly registered. Event monitoring will be required per Section 18.0 of the protocol.

13.9 Definition of Cancel

A patient is deemed a *cancel* if he/she is removed from the study for any reason before any study treatment is given. On-study material and the End of Active Treatment/Cancel Notification Form must be submitted. No further data submission is necessary.

14.0 Body Fluid Biospecimens

14.1 Summary Table of Research Blood and Body Fluid Specimens to be collected for this Protocol (see Appendix III for handling)

Correlative Study (Section for more information)	Mandatory or Optional	Blood or Body Fluid being Collected	Type of Collection Tube (color of tube top)	Volume to collect per tube (# of tubes to be collected)	Baseline	Cycles 1-4 Day 1 Pre- treatment	End of Cycle 12	End of treatment ²	At time of PMD or PD ²	
Tumor biopsy or bone marrow aspirate ¹	Mandatory	Tumor or bone marrow	ACD (yellow top)	6 mL (1 tube)	X					
Peripheral blood	Mandatory	Whole Blood	EDTA (purple top)	10 mL (4 tubes)		X	X	X	X	
Peripheral blood	Mandatory	Whole Blood	No anticoagulant (red top)	10 mL (1 tube)		X	X	X	X	

¹ Only obtained when a clinical biopsy/bone marrow is needed. Biopsies and bone marrow samples can be collected ≤ 90 days prior to registration provided there is no intervening treatment. If a biopsy or bone marrow was performed prior to consenting the patient for this study, a repeat biopsy or bone marrow is not required to obtain the research aspirate sample at baseline.

² Samples are required, however there is no protocol violation if sample is not obtained.

NOTE: All samples will be sent to Predolin Biobank Stable 613 (See Section 14.33)

14.2 Collection and Processing

14.21 Processing for the Blood, tumor and Marrow samples

Collection tube description and/or additive (color of tube top)	Component Available	Cell Surface Markers (Flow Cytometry)	DNA	Banking
EDTA (purple)	Plasma			X
EDTA (purple)	DNA		X	X
Serum -No anticoagulant (red)	Serum			X
ACD (yellow)	Tumor cells	X		X

14.22 Note: All collection tubes need to be labeled with the protocol number, patient initials (last, first middle), study patient ID number (if available), specimen type (bone marrow or peripheral blood) and date of collection.

14.3 Shipping and Handling

14.31 Kits

Kits will be provided for the samples collected in Section 14.1. The kit contains supplies and instructions for collecting, processing, and shipping specimens.

Participating Mayo sites may obtain kits by e-mailing [name] at [contact]. E-mail requests should include the site address, contact information and number of kits being requested.

Kits will be sent via FedEx® Ground at no additional cost to the participating institutions. Allow 3 to 4 business days to receive the kits.

Label specimen tubes with the protocol number, patient initials (last name, first name), study patient ID number (if available), specimen type (bone marrow or peripheral blood) and date of collection, as well as the arm of the study (A or B or C)

14.32 Collect all specimens according to instructions in Appendix III and table above.

14.33 Shipping Specimens

Specimens must be shipped the same day they are drawn.

Ship the bone marrow and peripheral blood tubes in the kit provided. No cold pack is required. The Fed Ex air bill is pre-addressed and provided in the kit.

Ship specimens via Priority Overnight service on Monday – Thursday Preferred (Friday only if you must) directly to:

Predolin Biobank

[REDACTED]

[REDACTED]

Rochester, MN [REDACTED]

Please email [REDACTED] or call [REDACTED] at [REDACTED] to notify the laboratory when specimens are being shipped. The message should include the study name, sample type, Fed Ex air bill tracking number, contact name and telephone number.

Shipping costs will be covered by the study if these kits and Fed Ex air bills are used for shipping specimens. Each kit contains the required tubes.

14.4 Background and Methodology

- 14.41 Blood/blood product samples will be collected for the following research
- 14.411 DNA extraction and storage of DNA for future pharmacogenetic assays (e.g., for genetic polymorphisms, neoantigens and mutational burden that may correlate with treatment efficacy). [name] laboratory Stable 6-28 will initially analyze a portion of the DNA using standard laboratory protocols. Remaining DNA will be stored frozen at -70°C by [name] Lab, according to patient consent information) until specific analyses are identified. As protocols are developed, they will be presented for IRB review and approval.
- 14.412 A portion of the serum/plasma/PBMCs will initially be analyzed for the presence of Cytokines and T-cell activation in [name] laboratory using standard laboratory protocols. According to patient consent information remaining serum/plasma will be stored frozen at -70°C by [name] Lab, until specific analyses are identified. As protocols are developed, they will be presented for IRB review and approval.
- Serum cytokine analysis: Samples will be subjected to multiplex ELISA (Invitrogen, Camarillo, CA) to measure 30 serum cytokines in pre-treatment and subsequent blood samples. Luminex-200 system version 1.7 will be used for reading plates and MasterPlex QT1.0 system (MiraiBio) will be used to analyze data. Cytokines will include epidermal growth factor (EGF), eotaxin, basic fibroblast growth factor (FGF-b), granulocyte macrophage colony stimulating factor (GM-CSF), hepatocyte growth factor (HGF), IFN- α , IFN- γ , interleukin 1 receptor antagonist (IL-1RA), IL-1 β , IL-2, IL-2R, IL-4, 5, 6, 7, 8, 10, 12, 13, 15, 17, Inducible protein-10 (IP10/CXCL10), monocyte chemotactic protein 1 (MCP-1), monokine induced by interferon γ , (MIG/CXCL9), MIP-1 α (CCL3), MIP1 β (CCL4), regulated on activation normal T-cell expressed and secreted (RANTES), TNF- α and vascular endothelial growth factor (VEGF). Internal control serum will be included in all assays to control for interassay variation.
- Flow cytometry: To define changes in peripheral blood cell populations (Activated vs, exhausted T-cells, Treg cells, monocytes and MDSCs) after treatment with nivolumab, peripheral blood mononuclear cells will be stained with fluorochrome-conjugated antibodies to human CD69 (R&D Systems), CD3 (clone HIT3a), CD19 (clone 4G7), PD1 (clone EH12.1), CD14 (clone M5E2), CD163 (clone GH1/61), CD21 (clone B-ly4), CD273 (clone M1H18), CD274 (clone M1H1), TIM3 (clone 344823), and CD23 (clone EBVCS-5; all obtained from BD Biosciences) and the data will be analyzed using CellQuest software (Becton Dickinson).
- 14.413 We will collect serum/plasma for future research studies, according to patient consent information on molecular determinants of efficacy and tolerability. Samples will be stored frozen at -70°C by [name] Lab until specific analyses are identified. As protocols are developed, they will be presented for IRB review and approval.

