2.2 Secondary

2.21 To assess safety and tolerability of the regimen in this patient population

2.22 To assess progression-free survival (PFS)

2.23 To assess duration of response (DOR)

2.24 To assess overall survival (OS)

2.3 Correlative Research

2.31 To evaluate T-cell/cytokine profile in the peripheral blood – peripheral blood specimens will be used to assess T-cell activation and cytokine up regulation as measures of treatment effect. This goal will be exploratory in nature and reported descriptively

- 2.32 To evaluate intratumoral Biomarkers- intratumoral cell populations and distribution, genetic variability, mutational burden and T-cell activation will be evaluated to identify potential biomarkers that correlate with response to therapy. This goal will also be exploratory in nature
- 2.33 To assess the potential association between PD-L1/PD-1/PD-L2 expression on tumor and T cells and/or PD-L1 soluble levels in plasma with clinical efficacy of PD-1 blockade.

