17.32 Paraffin Embedded Tissue

17.321 Paraffin embedded tissue block will be used to generate tumor derived genomic DNA for the correlative studies as described in section 17.4.

17.322 If tissue block is not available, then Ten (10) 4-5 micron paraffin embedded tissue slides will be collected for DNA isolation and sequencing.

17.323 Eight (8) 4-5 micron paraffin embedded tissue slides will be collected for staining cell specific markers for T cells, T cell subsets, tumors and PD-1, PD-L1, etc. other related co-stimulatory or inhibitory markers.

17.324 Shipping

Specimens need to be labeled with patient initials and study ID number, sex, age and specific diagnosis for the trial enrollment.

Ship specimens via Priority Overnight service on Monday – Thursday Preferred (Friday only if you must) directly to:

Predolin Biobank Attn: [REDACTED]

[REDACTED]
[REDACTED]
Rochester, MN [REDACTED]

Please email [REDACTED] or call [REDACTED] to notify the laboratory when specimens are being shipped. The message should include the study name, sample type, Fed Ex air bill tracking number, contact name and telephone number.

Shipping costs will be covered by the study.

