17.4 Background and Methodology

Background: Accumulating evidence has shown that clinical responses to checkpoint inhibitor is likely associated with tumor PD-L1 overexpression as well as tumor exomic mutation burden. Therefore, we plan to test the spectrum of tumor mutations using WES/targeted sequencing as well as measure tumor PD-L1 and other marker staining with immunohistochemistry analysis

- 17.41 **Sequencing:** Genomic DNA will be extracted from formalin-fixed, paraffin-embedded tissue blocks. H&E-stained sections from each case will be reviewed by an expert hematopathologist and representative blocks with at least 30% tumor cells will be selected. 10 x 5-micron sections will be cut from blocks in the Mayo Clinic Pathology Research Core (based on tissue area of 25 mm²). DNA will be extracted in the Mayo Clinic Biospecimens Accessioning and Processing Core using the Qiagen FFPE DNA extraction kit. DNA quantitation will be performed using a Qubit fluorometer prior to sequencing.
- 17.42 **Immunohistochemistry (IHC):** Expression of PD-L1 has been demonstrated to associate with clinical response of cancer patients treated with nivolumab. It is also established that CD8⁺ cytotoxic T cell response is critical to mediate anti-tumor immunity. Therefore, multiple markers including T cell, tumor cells, as well as related co-stimulatory and inhibitory markers will be stained to identify if there is any association of expression of these markers with clinical response. Serial 5- μ m paraffin-embedded sections will be used for IHC. The tissue will be deparaffinized with three changes of xylene and cleared through graded series of ethanol. Endogenous peroxidase will be quenched by incubation in 50% methanol/H₂O₂ and after rinsing with tap water; all sections will be pretreated for 30 minutes with 50 mmol/L EDTA using a steamer and cooled for additional 5 minutes. All staining will be done automatically on DAKO Autostainer using the following antibodies to CD11c (Leica Microsystems 5D11), CD14 (Cell Marque EPR 3653), CD163 (DAKO 1F8), CD68 (DAKO PG-M1), CXCL13 (R&D Systems 53610), FOXP3 (Abcam 236AE/7), CD3 (R&D Systems), PD-L1 (405.9A11), PD-L2 (366C.9E5) and PD-1 (Abcam NAT). The sections will be viewed with an Olympus BXFA51 microscope and pictures taken with an Olympus DP71 camera.

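### The listed blood flow panel cannot identify Treg cells or separate MDSCs from monocytes, and the tissue staining list has no CD8 although the CD8+ response is a stated reason for staining

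*Combined protocol and SAP*

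**What the plan says.** **Blood (Section 14.412, flow cytometry).** The stated purpose is "To define changes in peripheral blood cell populations (Activated vs, exhausted T-cells, Treg cells, monocytes and MDSCs) after treatment with nivolumab". The antibodies are "CD69 (R&D Systems), CD3 (clone HIT3a), CD19 (clone 4G7), PD1 (clone EH12.1), CD14 (clone M5E2), CD163 (clone GH1/61), CD21 (clone B-ly4") and "CD273 (clone M1H18), CD274 (clone M1H1), TIM3 (clone 344823), and CD23 (clone EBVCS-5; all obtained from BD Biosciences"). That is 7 + 4 = 11 antibodies.

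**Tissue (Sections 17.323 and 17.42).** Section 17.323 sets slides aside for "staining cell specific markers for T cells, T cell subsets, tumors and PD-1, PD-L1" and related markers, and its wording is open-ended. Section 17.42 motivates the staining by saying that the CD8+ "cytotoxic T cell response is critical to mediate anti-tumor immunity". It then says "All staining will be done automatically on DAKO Autostainer using the following antibodies to CD11c" and gives the list: "CD11c (Leica Microsystems 5D11), CD14 (Cell Marque EPR 3653), CD163 (DAKO 1F8), CD68 (DAKO PG-M1), CXCL13 (R&D Systems 53610), FOXP3 (Abcam 236AE/7"), followed by CD3, PD-L1, PD-L2 and PD-1. That is 6 + 4 = 10 antibodies.

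**Goals and analysis.** Goal 2.31 is T-cell activation and cytokines in blood. Goal 2.32 is intratumoral biomarkers. Goal 2.33 concerns PD-L1/PD-1/PD-L2 "expression on tumor and T cells and/or PD-L1 soluble levels in plasma" in relation to efficacy. Section 16.331 treats all of these as exploratory. It plans Fisher, Wilcoxon and log-rank comparisons that include intratumoral cell populations.

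**The concern.** A correlative aim can be met only if the assay returns the variable that the aim names. Here two blood populations and one tissue population are named or relied on, but no listed reagent identifies them. If the laboratory follows the text, there will be no Treg or distinct MDSC variable to summarize from blood. The intratumoral cell populations that Section 16.331 compares by outcome will include no CD8+ count.

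Timing matters more for blood than for tissue. Section 14.412 keeps left-over serum and plasma frozen but does not say so for PBMCs, and the table in 14.21 shows no banked PBMC component. As written, the pre-dose samples of Cycles 1 to 4 and the later samples may not be available for a corrected panel. The research samples are mandatory for patients (Sections 3.19b and 6.2), which is a further reason for the panel to match its purpose.

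**Working it through.** The plan attaches no figure, power or error rate to this point, so there is nothing to reproduce. The check sets each named population beside the listed antibodies. Which markers define a population is an assumption from general laboratory knowledge.

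**Blood, Section 14.412 (11 antibodies, 5 populations)**

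| Population named | Listed antibodies that bear on it | Identifiable as written |
|---|---|---|
| Activated T cells | CD3 with CD69 | Yes |
| Exhausted T cells | CD3 with PD1 and TIM3 | Yes |
| Treg cells | CD3 only; CD4, CD25, CD127 and FOXP3 absent | No |
| Monocytes | CD14, CD163 | Yes |
| MDSCs | CD14, shared with monocytes; HLA-DR, CD33, CD11b and CD15 absent | Not separable from monocytes |

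Count: 5 named, 3 identifiable, 5 − 3 = 2 not. If activated and exhausted T cells are counted as one contrast, it is 2 of 4.

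CD14 is a partial MDSC marker, so it would be too strong to say that the panel has none. That does not change the result: a signal common to two named populations cannot report a change in one as distinct from the other.

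**Tissue, Section 17.42 (10 antibodies)**

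| Target | Listed antibodies | Covered |
|---|---|---|
| All T cells | CD3 | Yes |
| FOXP3+ cells | FOXP3 | Yes |
| Macrophages and other myeloid cells | CD11c, CD14, CD163, CD68 | Yes |
| PD-1, PD-L1, PD-L2 overall | One antibody each | Yes |
| CD8+ T cells | None | No (0 of 10) |

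CD8 cannot be recovered by subtraction. CD3+ cells less FOXP3+ cells would still include other T cells, since CD4 is not listed either. In the T-cell histologies admitted by Section 3.12 they could include the tumor itself.

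**Internal comparison.** FOXP3 is in the tissue list and not in the blood list, although Treg cells are named as a target only for blood. This is the one piece of support that does not rest on outside knowledge of markers.

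**Reach into the design.** The decision rules in Section 16.2 (at least 2 responses in 12 to continue, at least 6 in 35 to recommend further study) use response counts only. No marker enters them, so the tabulated power and early-stopping probabilities are unaffected.

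**The case against.** *The correlates are exploratory.* Goals 2.31 and 2.32 and Section 16.331 say so, and 2.31 is descriptive. This stands and limits the importance of the point. It does not make the panel fit its stated purpose.

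*The tissue list may not be exhaustive.* Section 17.323 is open-ended, and a retained block (the preferred submission in 17.1) could be cut again for CD8. This stands in part. However, 17.42 says that all staining uses the antibodies it then lists, and re-cutting does not help where only slides were sent. The blood list has no such open wording.

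*The documents give no gating definitions.* True, and the Treg and MDSC results rest on that assumption.

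A reader might also infer stronger claims that the documents do not support:

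- **That the immune correlates as a whole fail, or that goals 2.31 to 2.33 cannot be answered.** Goal 2.31 is served by CD3 with CD69 and by the 30-cytokine assay. Sequencing (17.41) serves the genetic part of 2.32. PD-1, PD-L1 and PD-L2 have immunohistochemistry, and the 9p24.1 region has FISH (17.43).
- **That the absence of CD8 from the blood panel is a contradiction.** Section 14.412 does not name CD8+ cells as a blood target.
- **That soluble PD-L1 is required but has no assay.** Goal 2.33 words it as an alternative or addition. Sections 14.412 and 14.413 keep plasma for analyses to be specified later.
- **That PD-1/PD-L1 cannot be split between tumor and T cells.** Table 14.21 assigns tumor cells to flow cytometry, 17.23 collects immunophenotyping reports where available for cases sent to central review, and 17.323 leaves room for further markers. What is missing is only a statement of how the split will be scored.

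**Conclusion.** The point holds in a narrow form. As listed, the blood panel cannot identify Treg cells and cannot separate MDSCs from monocytes, which is two of its five named populations. The tissue list omits CD8 although the CD8+ response is a stated reason for the staining. This is more than missing detail, because the assays run as written would not return readouts that the text sets out or relies on.

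The conclusion assumes conventional marker definitions and that the two lists are what the laboratory will run. The consequence is confined to exploratory correlates. The response endpoint, sample size, error rates and secondary clinical endpoints are untouched.

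**What to change.** 1. **Section 14.412:** add a Treg set (for example CD4 with CD25/CD127, or with FOXP3) and a minimal MDSC set (for example HLA-DR, CD33 and CD11b), and state the gating definition of each population. Otherwise delete Treg cells and MDSCs from the stated purpose.
2. **Section 17.42:** add CD8, or remove the CD8+ response as a reason for staining.
3. **Preferably, in 17.42:** state how PD-1 and PD-L1 will be scored on tumor and on reactive T cells, since CD3 alone does not separate them in a T-cell lymphoma.

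The cost is a few reagents in assays already planned, plus protocol wording; no new patient procedure is needed. If flow channels are limiting, an existing marker may have to be swapped out. No B-cell population is named in 14.412, so CD19, CD21 and CD23 could be looked at first, but the documents do not say why they are there and the choice belongs to the laboratory. In tissue, CD8 makes 10 + 1 = 11 antibodies against the eight staining slides in 17.323. Where no block is released, an order of priority should therefore be set in advance. The blood change should be made before PBMCs are used.

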15.0 Drug Information

15.1 Nivolumab (Opdivo®, BMS-936558)

- 15.11 **Background:** Nivolumab is a human immunoglobulin G4 (IgG4) monoclonal antibody that selectively inhibits programmed cell death-1 (PD-1) activity by binding to the PD-1 receptor to block the ligands PD-L1 and PD-L2 from binding. The negative PD-1 receptor signaling that regulates T-cell activation and proliferation is therefore disrupted. This releases PD-1 pathway-mediated inhibition of the immune response, including the antitumor immune response.
- 15.12 **Formulation:** Available for injection 10mg/ml (4mL, 10mL) in a single-use vial [contains in sodium citrate, sodium chloride, mannitol, diethylenetriaminepentacetic acid (pentetic acid), and polysorbate 80]
- 15.13 **Preparation and storage:** Appropriate dose/required volume should be added to an IV container of either 0.9% Sodium Chloride or 5% Dextrose in Water with a final concentration of 0.35 mg/ml to 10 mg/ml. Mix diluted solution by gentle inversion. Do not shake. Discard partially used vials or empty vials. Store at room temperature for no more than 8 hours (includes time of administration) or under refrigeration at 2°C to 8°C (36°F-46°F) for no more than 24 hours from the time of infusion preparation. Protect from light and freezing.
- 15.14 **Administration:** Administer over 60 minutes through a line with a sterile, nonpyrogenic, low protein binding 0.2 to 1.2 micrometer in-line filter. Establishing that nivolumab can be safely administered using a shorter infusion time (30 minutes) is under investigation. It cannot be administered as an IV push or bolus injection. Do not administer other medications through the same IV line. Flush IV line at the end of the infusion.
- 15.15 **Pharmacokinetic information:**
Distribution: Vd: 8 L
Half-life elimination: ~27days
Renal Impairment: No clinically important differences in the clearance of nivolumab were found between subjects with mild or moderate renal impairment and subjects with normal renal function. Data from subjects with severe renal impairment are too limited to draw conclusions on this population.
Hepatic Impairment: No clinically important differences in the clearance of nivolumab were found between subjects with mild hepatic impairment and normal hepatic function. Nivolumab has not been studied in subjects with moderate (total bilirubin >1.5 to 3 times ULN and any AST) or severe hepatic impairment (total bilirubin >3 times ULN and any AST).
- 15.16 **Potential Drug Interactions:** No formal pharmacokinetic drug-drug interaction studies have been conducted.
- 15.17 **Known potential toxicities:** Consult the package insert for the most current and complete information.
Very common known potential toxicities, ≥10%:
Gastrointestinal: Diarrhea
General: Fatigue
Less common known potential toxicities, 1% - 10%:
Endocrine: Hypothyroidism, hyperthyroidism, hyperglycemia
Gastrointestinal: Nausea, vomiting, constipation, abdominal pain, stomatitis, dry

mouth, colitis,

General: Pyrexia, asthenia, peripheral edema, chills,

Immune system: infusion related reaction

Investigations: Increased AST/ALT, increased lipase, increased alkaline phosphatase, increased creatinine, increased amylase, increased thyroid stimulating hormone

Metabolism and nutrition disorders: Decreased appetite, hyponatremia

Musculoskeletal: Arthralgia, myalgia, back pain, pain in extremities

Nervous system: Headache, dizziness

Respiratory: Pneumonitis, dyspnea, cough

Skin and subcutaneous tissue disorders: Pruritis, rash, dry skin, maculopapular rash, vitiligo, erythema, generalized pruritus

Uncommon known potential toxicities, 0.1%-<1%:

Cardiac: Tachycardia, atrial fibrillation

Ear: Vertigo

Endocrine and metabolic: Adrenal insufficiency, thyroiditis, hypophysitis, diabetes mellitus, hypopituitarism, autoimmune thyroiditis

Eye: Dry eye, blurred vision, uveitis

Gastrointestinal: Pancreatitis, gastritis

General: Mucosal inflammation, edema, face edema, localized edema, peripheral swelling, swelling face

Hepatic: Hepatitis, autoimmune hepatitis,

Immune system: Hypersensitivity,

Infections: Upper respiratory tract infection, bronchitis

Investigations: increased bilirubin

Musculoskeletal: Musculoskeletal pain, arthritis, musculoskeletal chest pain, neck pain, polyarthritis, bones pain

Nervous system: Peripheral neuropathy, peripheral sensory neuropathy, peripheral motor neuropathy

Renal and urinary: Acute kidney injury; renal failure, tubulointerstitial nephritis

Respiratory: Respiratory failure, interstitial lung disease, lung infiltration

Skin and subcutaneous tissue disorders: Alopecia, dermatitis acneiform, urticaria, psoriasis, dermatitis, rash (pruritic, macular, erythematous, generalized, popular, pustular), drug eruption

Vascular: Hypotension, hypertension

Rare known potential toxicities, < 0.1% (Limited to life-threatening):

Cardiac: Arrhythmia, ventricular arrhythmia

Endocrine: Diabetic ketoacidosis, autoimmune hypothyroidism

Eye disorders: iridocyclitis

Gastrointestinal: Autoimmune colitis, acute pancreatitis

Hepatic: Acute hepatitis

Immune system: Anaphylactic reaction, sarcoidosis

Musculoskeletal: Myositis, myocarditis, polymyalgia rheumatic, polymyositis, rhabdomyolysis

Nervous system: Polyneuropathy, encephalitis, Myasthenia gravis, Guillain-Barre syndrome, demyelinating polyneuropathy, demyelination, myasthenic syndrome

Renal: Nephritis, autoimmune nephritis

Respiratory: Pneumonia, acute respiratory distress syndrome
Skin and subcutaneous tissue disorders: Erythema multiforme, Stevens Johnson syndrome, toxic epidermal necrolysis
Other: Solid organ and tissue transplant rejection, graft versus host disease, increased risk of transplant-related complications

15.18 **Drug procurement:** Investigational nivolumab is provided free of charge to patients by Bristol-Myers Squibb Research and Development.

15.19 **Nursing Guidelines**

- 15.191 Nivolumab side effects vary greatly from those of traditional chemotherapy and can vary in severity from mild to life threatening. Instruct patients to report any side effects to the study team immediately. Side effects may be immediate or delayed up to months after discontinuation of therapy. Most side effects are reversible with prompt intervention of corticosteroids. Additionally combination therapy (with ipilimumab) tends to have a higher rate of immune mediated side effects.
- 15.192 Diarrhea can be common and can be very severe, leading to colonic perforation. Instruct patients to report ANY increase in the number of stools and/or change in baseline, blood in the stool, abdominal pain to the study team immediately.
- 15.193 Rash/pruritis/dermatitis is seen. Patients should report any rash to the study team. Treat per section 8.0 and monitor for effectiveness.
- 15.194 Monitor LFTs closely as elevations in these levels could indicate early onset autoimmune hepatitis. Patients should also be instructed to report any jaundice, or right upper quadrant pain to the study team immediately.
- 15.195 Pneumonitis can be seen and may be mild (only seen on imaging) to severe. Patients should be instructed to report any SOB, dyspnea, cough, chest pain, etc. to the study team immediately. Patients reporting these symptoms should have a pulse ox checked and consider immediate imaging per the treating MD.
- 15.196 Endocrinopathies (including hypopituitarism, hypothyroidism, hypophysitis, new onset diabetes, and adrenal insufficiency) are seen with this agent. Patients may present only with the vague sense of fatigue and “not feeling well.” Additional symptoms may be that of nausea, sweating, headache and decreased activity tolerance. Instruct patients to report these signs or symptoms immediately and obtain appropriate labs as ordered by MD.
- 15.197 Pancreatitis is possible with nivolumab. Instruct patients to report abdominal pain, nausea and vomiting to the study team.
- 15.198 Patients who are started on steroid therapy for any side effects of nivolumab toxicity should be instructed to take the steroids as ordered, and not to discontinue abruptly as symptoms may return and be severe. Patients may be on steroid therapy for weeks. Instruct patients to report any increase or change in side effects with any dosage decrease as patients may need a slower taper.

- 15.199a Monitor renal functions as patients may experience acute interstitial nephritis. Report any increase of levels to the study team.
- 15.199b Patients who have previously undergone a solid organ or tissue transplant and subsequently undergo therapy with nivolumab are at increased risk of organ/tissue rejection. Instruct patients that it is crucial that they stay in touch with their transplant team during treatment.
- 15.199c Patients who have undergone allogeneic BMT are at higher risk of GVHD and death when receiving nivolumab. Monitor patients closely for GVHD symptoms and instruct patients to report these symptoms to the study team immediately.

